
myDAVjpNi

Protocol v3.0 15FEB2021

	
 • Procurement of tumor tissue using a VacuCut® biopsy needle (or punch biopsy) will be performed on day 3 and before every intratumoral study drug administration (Q2W). • End-of the study treatment phase 
 • Study treatment will be discontinued at any time during the study at the diagnosis of progressive disease per iRECIST response assessment criteria, unacceptable adverse event(s), or patient withdrawal of consent to continue study treatment, lost-to-follow-up or death. • Patients will be considered “off-study treatment” and enter the follow-up phase after the safety-follow-up visit 30 (+7) days after the date of the last administration of study treatment). • Follow-up phase: 
 • A safety follow-up visit will be performed approximately 30 (+7) days after the last administration of study treatment. • Patients who have ended study treatment and experience no ongoing treatment related AEs of grade >2 will be followed-up for survival for 3 years following enrollment to the study. • Patients who end study treatment without progression of disease will also be followed-up for their disease status for 3 years following enrollment to the study. • During the follow-up phase the frequency and nature of investigations will be at the discretion of the treating physician and data will be captured from the medical file of the patient or through inquiry of their treating physician.
Assessments during the treatment-phase	
 • Safety will be monitored on a continuous basis. • A tumor biopsy (VacuCut® needle or punch biopsy) will be performed before every injection of AS01 and ipilimumab (if feasible). • Blood analyses (incl. routine chemistry- and hematology parameters) will be obtained on day 15 and prior to every administration of the study treatment. • Tumor response will be assessed by total body PET/CT in week 12 and every 12 weeks thereafter.

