8.14. Discontinuation of Subjects Following any Treatment with Study Drug

For more information see original protocol version.

9. Study procedures

The Schedule of Assessments is summarized in Table 1

myDAVlpNi

Protocol v3.0 15FEB2021

Table 1 Assessments made during the study

	Screening	Treatment phase (week number & day)					Follow-up phase	
Study Procedures	≤ -28 Days ¹	Day 1	Day 2	Day 3	Day 15 + and every other +14 days up to day 71 (=d1W11)	Day 15, and every other +14 days up to day 365	Safety ²	Survival ³
General Assessments								
Informed Consent	X							
Review of Eligibility Criteria	X							
Demographics, Medical, Surgical and Medication History	X							
Recording of Concomitant Medication	↔	↔	↔	↔	↔	↔	X	
Vital Signs ⁴	X						X	
Physical Exam Including Body Weight	X						X	
ECOG Performance Status	X						X	
12-lead electrocardiogram (ECG) ⁵	X						X	
Review of AEs and SAEs ⁶	↔	↔	↔	↔	↔	↔	X	X
Survival Assessment								X
Treatment Administration								
AS01 and Ipilimumab intratumoral ⁷		X			X			
Nivolumab IV ⁷		X				X		
CD1c(BDCA-1) ⁷ /CD141(BDCA-3) ⁷ myDC ⁸			X					

¹ Procedures to be performed ≤ 28 days prior to enrollment.

² Safety follow-up will be performed approximately 30 (+7) days after the last dose of study treatment.

³ Subjects will be followed for survival from the date of the safety follow-up visit until up to 36 months after the date of recruitment of the last subject.

⁴ Vital signs (systolic/diastolic blood pressure, heart beat, and temperature) must be performed prior to the study treatment (AS01, Ipilimumab, and Nivolumab and/or CD1c(BDCA-1)⁷/CD141(BDCA-3)⁷ myDC administration), and at the safety follow-up.

⁵ A single 12-lead ECG will be performed ≤ 28 days before enrollment and the safety follow-up visit.

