²² Radiographic imaging (whole body PET/CT, plus MRI of the brain if clinically indicated) is required at screening. Tumor assessments must include all known sites of disease. The screening scans must be done within 28 days prior to enrollment. During treatment, radiographic imaging (whole body PET/CT, plus MRI of the brain if clinically indicated), will be performed at week 13 and every 12 weeks thereafter or more frequently if clinically indicated until confirmed PD per iRECIST or start of new anticancer treatment. Imaging should not be adjusted for cycle initiation delays and performed according to the calendar. The imaging modality selected (e.g., PET/CT or MRI) should remain constant for any individual subject. Response or progression should be confirmed by repeated radiographic imaging ≥ 4 weeks after the first indication of response or progression. Radiographic imaging is not required at the safety follow up visit. For subjects who discontinued treatment for any reason other than confirmed PD, every effort should be made to complete radiographic assessments every 12 weeks (+1 week) or more frequently if clinically indicated during the long-term follow-up until documentation of confirmed PD per iRECIST, start of new anticancer therapy, or end of study, whichever occurs first. Subjects who have reached a confirmed CR may increase their interval of radiographic assessments up to 6 months after the first 2 years beyond confirmed CR.

²³ Tumor response assessment by whole body PET/CT and complementary medical imaging as indicated should be performed in week 13 and every 12 weeks thereafter until the end of the study treatment phase.

myDAvlpNi

Protocol v3.0 15FEB2021

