10.2. Safety Follow-up Visit

Upon permanent discontinuation from the study treatment for any reason, the following procedures will be performed approximately 30 (+7) days after the last dose of IT ipilimumab, and IV nivolumab:

- Vital signs (systolic/diastolic blood pressure, heart rate, temperature): should be documented on the vital sign electronic data record.
- Physical examination including body weight as per standard of care
- ECOG performance status assessment
- Local laboratory Assessments
 - Hematology panel: hemoglobin, hematocrit, WBC count with 5-part differential (3-part differential if 5-part unable to be performed), RBC count, platelets
 - Chemistry panel: sodium, potassium, chloride, calcium, magnesium, phosphorus, uric acid, total protein, albumin, ureum, creatinine, total bilirubin, alkaline phosphatase, AST, ALT, glucose
 - Thyroid function tests: FT4, TSH
 - Serum pregnancy test for female subjects of childbearing potential
 - Urinalysis (blood, glucose, protein) and reflexive microscopic exam only for any abnormal urinalysis results
- Recording of adverse events
- Recording of serious adverse events: Serious adverse events that occur within 90 (+7) days after the cessation of all study treatment or 30 (+7) days following cessation of treatment if the subject initiates new anticancer therapy, whichever is earlier, will be reported within 24 hours following the investigator's knowledge of the event.
- Documentation of concomitant medications
- Radiographic tumor imaging, clinical tumor assessment, photographic assessment, and tumor response assessments are to be performed if the subject ended study treatment prior to confirmed PD per iRECIST and has not had assessments performed within 4 weeks (+1 week) of the visit.
- Radiographic tumor imaging assessments must include whole body PET/CT. MRI of the brain will only be performed if signs or symptoms suggestive of CNS metastasis are present.
- Photographic imaging assessments of visible cutaneous and subcutaneous:
 - Photographs of visible cutaneous and subcutaneous index tumor lesions and of new visible lesion cutaneous and subcutaneous, if present.
 - Note: When a tumor lesion can be accurately evaluated by both, radiographic imaging and photographs, radiographic imaging evaluations should be undertaken.
- Clinical tumor assessments must include clinical measurement of cutaneous, subcutaneous, or palpable nodal tumor lesions by caliper. Note: When a tumor lesion can be accurately

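### The synopsis and Table 1 set conflicting follow-up rules, and the synopsis rule, applied literally, opens overall survival to informative loss.

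*Supplement*

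**What the plan says.** Four pairs of statements in v3.0 bear on follow-up.

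- **Who is followed for survival.** Section 3 (Study Synopsis, follow-up phase): "Patients who have ended study treatment and experience no ongoing treatment related AEs of grade >2 will be followed-up for survival". Section 9, Table 1, footnote 3, puts no adverse-event (AE) condition on the subjects it follows.
- **For how long.** The synopsis says these patients "will be followed-up for survival for 3 years following enrollment to the study". Footnote 3 runs "until up to 36 months after the date of recruitment of the last subject".
- **Assessments after treatment ends.** The synopsis keeps patients who stop without progression under disease-status follow-up for 3 years from enrolment, with no AE condition, but adds: "During the follow-up phase the frequency and nature of investigations will be at the discretion of the treating physician". Table 1, footnote 22, says of patients who stop for a reason other than confirmed progression that "every effort should be made to complete radiographic assessments every 12 weeks (+1 week". Footnotes 20 and 21 ask the same for clinical measurements and photographs.
- **Imaging at the safety visit.** Footnote 22: "Radiographic imaging is not required at the safety follow up visit". Section 10.2: "Radiographic tumor imaging, clinical tumor assessment, photographic assessment, and tumor response assessments are to be performed if the subject ended study treatment" before confirmed progression and there has been no assessment within 4 weeks (+1 week).

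OS is a secondary endpoint in the synopsis but is not listed in Section 5.4. Progression-free survival (PFS) and response duration are secondary in both places. Sections 7.4 (follow-up phase), 10.3 (long-term follow-up) and 14.1 (statistical analysis) only refer to the original protocol, which is not among the documents.

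**The concern.** The synopsis condition selects patients into survival follow-up by something that happens after treatment starts and may well be related to death. If a patient with an unresolved treatment-related AE above grade 2 is never entered, or is censored at the end of treatment, the loss is informative. The remaining patients then no longer represent the treated cohort for OS.

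The assessment conflict affects other endpoints. Under Table 1, footnote 7, dosing also ends at complete response, disappearance of the injected lesion, intolerance, or 12 months. The patients with the longest disease control are therefore likely to leave treatment without progression, and they largely determine response duration and late PFS. If their scans follow clinical discretion, recorded progression dates depend on when someone chose to look.

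With at most 6 patients, one missing survival time or one poorly dated progression is visible in the result. Site staff also cannot follow both sets of rules.

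**Working it through.** The plan gives no figure to reproduce on this point: the sample size of 6 is not derived from a formula, and no test or event count depends on follow-up. The check compares the rules and sizes each difference where the documents allow.

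**Inputs**
- Maximum of 6 patients in one cohort (Section 14).
- Recruitment from 1 April 2021 to an estimated 31 December 2021 (synopsis, study period).
- Time limits of 3 years from own enrolment (synopsis) and up to 36 months after the last recruitment (footnote 3).
- Nivolumab for up to 12 months (Table 1, footnote 7).
- Rate of ongoing treatment-related AEs above grade 2: not given, so assumed over a range.

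**1. Who is followed.** One patient is 1/6 = 16.7% of the cohort. If each patient has probability p of an ongoing related AE above grade 2, independently, the chance that at least one of 6 meets the synopsis exclusion is 1 − (1 − p)^6:

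| Assumed p | Chance of at least one in 6 |
|---|---|
| 5% | 1 − 0.95^6 = 26% |
| 10% | 1 − 0.90^6 = 47% |
| 20% | 1 − 0.80^6 = 74% |
| 30% | 1 − 0.70^6 = 88% |

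Suppose such a patient dies, the death is not recorded and the patient is left out. With 2 patients alive at 3 years, the survival proportion moves from 2/6 = 33% to 2/5 = 40%. With 5 alive it moves from 5/6 = 83% to 5/5 = 100%. These are illustrations, not predictions.

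**2. For how long.** The recruitment window is 274 days, and 274 / 30.4375 = 9.0 months. A patient enrolled on the first day is followed for 36 months under the synopsis and up to 36 + 9 = 45 months under Table 1. For the last patient the two rules give the same date. A calendar cut-off of this kind is administrative censoring: it changes how mature the data are and does not by itself bias them.

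**3. Off-treatment assessments.** A patient who completes 12 months of treatment without progression has about 2 years left under the synopsis limit. Twelve-weekly assessment gives 104 / 12 = 8.7, so 8 to 9 assessments. The synopsis fixes none. No size can be put on the resulting delay in progression dates, because the documents give no discretionary interval.

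**4. Safety-visit imaging.** Footnote 22 does not require it, whereas Section 10.2 does for patients who stopped before confirmed progression without a recent assessment. These texts are directly opposed for that group.

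**Which endpoint each conflict touches**

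| Conflict | OS | PFS and response duration |
|---|---|---|
| AE condition | open to informative loss | not affected: the disease-status sentence carries no such condition |
| Time limit | maturity only | not a source of bias |
| Discretion versus 12-weekly | not affected | open to irregular assessment, in patients who stop without progression |
| Safety-visit scan | not affected | may change when progression is recorded in the same group |

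**The case against.** The strongest reply is that the AE condition stands in one synopsis sentence only. Footnote 3 has no such condition, and the survival column of Table 1 is marked for AE review as well as for survival, so having an AE does not remove a patient from that phase. The synopsis does not say that patients with ongoing severe AEs are dropped. It is silent about them, and its wording also fits continued safety follow-up until resolution, followed by survival-only contact. The follow-up and analysis sections that might settle this are in a protocol that is not shown.

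Much of this stands, and it rules out the stronger reading that a reader might infer, namely that OS, PFS and response duration are all biased. The AE condition cannot reach PFS or response duration. The footnotes ask for every effort after treatment ends, which is softer than a requirement, so the contrast is between best effort and discretion. Section 5.1 expects survival below 1 year in most cases, so few patients may reach either time limit.

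A reader might also infer that toxic deaths would be missed by the safety endpoint. That is not supported either. Serious AEs are collected after treatment ends without regard to AE status, for up to 90 (+7) days (Table 1, footnote 6; Section 10.2), and the primary endpoint does not use the OS rule.

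The contradiction itself remains. No text shown gives a patient with an unresolved AE a route into the OS data under the synopsis wording once that window closes. A reference to another protocol does not tell staff which of two rules in the current one applies.

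**Conclusion.** The follow-up rules in v3.0 conflict on four counts: who is followed for survival, for how long, how often disease is assessed off treatment, and whether a scan is due at the safety visit. If the synopsis is applied literally, OS is open to informative loss, and PFS and response duration are open to irregular assessment in patients who stop without progression. The time-limit conflict is worth up to 9 months for the earliest patient and affects maturity only.

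Bias is a risk under one of two stated rules; the documents do not show that it occurs. Its size for OS depends on the unknown rate of ongoing severe related AEs (26% to 88% chance of at least one affected patient, for assumed rates of 5% to 30%) and on whether those patients' deaths would go unrecorded. The consequence is for the completeness and interpretability of secondary endpoints in a cohort of at most 6. The primary safety endpoint is untouched, and no formal test shown depends on these data. The point deserves correction because it is easy to mend and a single lost patient cannot be averaged out.

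**What to change.** 1. Remove the AE condition from the synopsis sentence, so that every treated patient is followed for survival whatever the AE status, as footnote 3 already implies.
2. State one time limit in both the synopsis and Table 1. Taking the one in Table 1 adds up to 9 months of status checks for the earliest patient.
3. For patients off treatment without confirmed progression, reconcile the sentence on physician discretion with the best-effort 12-weekly schedule in footnotes 20 to 22. Citing that schedule in the synopsis is enough. It need not become a fixed obligation, which would add scheduled PET/CT scans.
4. Reconcile footnote 22 with Section 10.2 on imaging at the safety visit.

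Items 1 and 2 are almost free, since the synopsis already takes follow-up data from the medical file or by inquiry to the treating physician. Items 3 and 4 are wording changes, provided the off-treatment schedule stays on a best-effort basis. If item 4 is settled in favour of Section 10.2, the cost is a scan already foreseen there for a limited group.

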2.1.2. Sample size

For this amendment we will recruit six study patients to cohort-2. There will be no dose escalation regarding the number of myDC injected. The number of cells (and corresponding volume of cell suspension) will be determined by the size of the injected metastasis (see table). Patients with a tumor volume of $\geq 4\text{cm}$ (: sum of longest diameters of injected lesions) will receive all isolated CD1c (BDCA-1)⁺ / CD141 (BDCA-3)⁺ myDC.

myDAVlpNi

Protocol v3.0 15FEB2021

3. Study Synopsis

Study Title	Phase I clinical trial on intratumoral administration of autologous CD1c (BDCA-1)+ / CD141 (BDCA-3)+ myeloid dendritic cells plus ipilimumab and AS01 in combination with intravenously administered nivolumab
Study Design	Open label, single-center, phase I clinical trial
Study Sponsor	Universitair Ziekenhuis Brussel (UZ Brussel)
Principle Investigator	[name], MD PhD Medische Oncologie Universitair Ziekenhuis Brussel (UZ Brussel) [name] België [contact] Email: [contact]

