Summary of key eligibility criteria	
 • Histologically confirmed solid tumor • Metastatic disease that is progressive following standard of care • Skin, lymph node or other soft tissue metastases that can be injected by manual palpation, or by US- or CT-guidance • Availability of a pre-treatment tumor tissue biopsy (either as a representative archival sample or from a new tissue sample obtained by core needle biopsy or surgically excision) • No contra-indication for the collection of 500 ml of venous blood 	
Primary Objectives and Endpoints	
 • Objective: To document the safety of intratumoral injection of autologous CD1c (BDCA-1)⁺ / CD141 (BDCA-3)⁺ myDC co-product (isolated from PBMC) plus AS01, and ipilimumab (anti-CTLA-4 IgG₁ mAb) in combination with IV administration of nivolumab (anti- 	
 • Endpoint: Adverse events occurring in patients treated in this phase I clinical trial (collected on a continuous basis). Type, frequency and severity (graded according to the CTCAEv5.0) will be reported descriptively.

myDAVjpNi	Protocol v3.0 15FEB2021
-----------	-------------------------

	PD1 IgG ₄ mAb).	
Secondary Objectives/ Endpoint	
 Feasibility 	
 Percentage of study patients that can receive the planned CD1c (BDCA-1)⁺ / CD141 (BDCA-3)⁺ myDC intratumoral injection.
	
 Treatment disposition 	
 Number/volume of administered CD1c (BDCA-1)⁺ / CD141 (BDCA-3)⁺ myDC Administered dose of AS01, ipilimumab, and nivolumab
	
 Anti-tumor activity 	
 Tumor response (ORR) according to RECISTv1.1 and iRECIST Tumor response and duration of response of CD1c (BDCA-1)⁺ / CD141 (BDCA-3)⁺ myDC, AS01, and ipilimumab injected and non-injected metastases (reported descriptively)
	
 Progression-free survival (PFS) 	
 Time from first study treatment administration to progression of disease according to RECISTv1.1 and iRECIST (and possibly itRECIST)
	
 Overall survival 	
 Time from first first study treatment administration to death

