CD1c (BDCA-1) ⁺ / CD141 (BDCA-3) ⁺ myDC cell product	
Following transfer of the PBMC collected by leukapheresis, CD1c (BDCA-1)⁺ myDC and CD141 (BDCA-3)⁺ myDC will be isolated after depletion of CD14⁺ and CD19⁺ cells from the apheresis product using the CD1c (BDCA-1)⁺ / CD141 (BDCA-3)⁺ Dendritic Cell Isolation Kit on the CliniMACS Prodigy® isolation system (Miltenyi Biotec, Bergisch Gladbach, Germany). First, B cells are depleted using magnetic bead-coupled CD19 antibodies, followed by positive selection of CD1c (BDCA-1)⁺ myDC and CD141 (BDCA-3)⁺ myDC with biotin-coated CD1c and CD141 antibodies and magnetic bead-coupled anti-biotin antibodies. This procedure is expected to result in purified myDC, with an average purity of 63% and a yield between 20x10⁶ and 70x10⁶ cells. Following their isolation, CD1c (BDCA-1)⁺ / CD141 (BDCA-3)⁺ myDC will be transferred for administration to the patient.
 
CD1c (BDCA-1)⁺ / CD141 (BDCA-3)⁺ myDC cell products will need to meet the following release criteria: a minimal yield of 10 x 10⁶ CD1c (BDCA-1)⁺ / CD141 (BDCA-3)⁺ myDC (total number of cells), >50% viability and >50% purity.
 
The CD1c (BDCA-1)⁺ / CD141 (BDCA-3)⁺ myDC cell products will be provided as a cell suspension for intratumoral injection at a minimal

myDAVipNi	Protocol v3.0 15FEB2021
-----------	-------------------------

	concentration of $0,25 \times 10^6$ myDC cells/ml and a maximal concentration of 10×10^6 myDC cells/ml. A minimal total of 1×10^6 CD1c (BDCA-1) ⁺ / CD141 (BDCA-3) ⁺ myDC (= 4 ml of a $0,25 \times 10^6$ myDC cells/ml suspension) and a maximum total of 40×10^6 myDC (= 4 ml of a 10×10^6 CD1c (BDCA-1) ⁺ / CD141 (BDCA-3) ⁺ myDC cells/ml suspension) will be injected.
CD1c (BDCA-1) ⁺ /CD141 (BDCA-3) ⁺ myDC administration	
 Total administered CD1c (BDCA-1)⁺ /CD141 (BDCA-3)⁺ myDC volume will be up to 4.0 mL per patient. Injected volume per lesion will range from 0.1 mL for lesions ≤ 0.5 cm to 4.0 mL for lesions ≥ 5 cm in longest diameter. Injection of all lesions in individual patients will not be required. Determination of CD1c (BDCA-1)⁺ / CD141 (BDCA-3)⁺ myDC injection volume based on lesion size 
 > 5 cm up to 4 mL > 2.5 cm to 5 cm up to 2 mL > 1.5 cm to 2.5 cm up to 1 mL > 0.5 cm to 1.5 cm up to 0.5 mL

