8.2. Isolation of CD1c (BDCA-1)⁺ myDC / CD141 (BDCA-3)⁺ myDC

First, CD14⁺ and CD19⁺ cells will be depleted from the PBMC product using murine anti-CD14 and anti-CD19 monoclonal antibodies conjugated to superparamagnetic iron dextran particles. This step is followed by the simultaneous isolation of CD1c (BDCA-1)⁺ and CD141 (BDCA-3)⁺ myDC using a combination of a BDCA-1 specific monoclonal antibody and a BDCA-3 specific monoclonal antibody, both biotin-conjugated (Miltenyi Biotec, Bergisch Gladbach, Germany). After labeling with the CliniMACS Anti-Biotin Reagent, the target cells are immunomagnetically enriched. In a final step, the isolated BDCA-1⁺ / BDCA-3⁺ dendritic cell fraction will be concentrated by centrifugation and resuspended in PBS/EDTA (Miltenyi) containing 0.5%

myDAVjpNi

Protocol v3.0 15FEB2021

human albumin to obtain a cell suspension at the concentration (cells/ml) desired for clinical administration. *See also the IMPD file.*

Following their isolation, CD1c(BDCA-1)⁺ / CD141(BDCA-3)⁺ myDC will be transferred for administration to the patient. CD1c(BDCA-1)⁺ / CD141(BDCA-3)⁺ myDC cell products will need to meet the following release criteria: >50% cell viability and >50% cell purity.

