8.3. Intratumoral injection of CD1c (BDCA-1)⁺ myDC / CD141 (BDCA-3)⁺ myDC product

The CD1c (BDCA-1)⁺ myDC / CD141 (BDCA-3)⁺ myDC product will be administered by intratumoral injection in the lesions that were injected with AS01 on day 1 (approximately 24 hours after intratumoral injection of AS01).

The total administered CD1c (BDCA-1)⁺ myDC / CD141 (BDCA-3)⁺ myDC volume will be up to 4.0 mL per intratumoral treatment session. Injected volume per lesion (skin-, soft tissue or lymph-node metastase(s)) will range from 0.1 mL for lesions < 0,5 cm to 4.0 mL for lesions > 5 cm in longest diameter. Injection of all lesions in an individual patient will not be required.

The determination of CD1c (BDCA-1)⁺ myDC / CD141 (BDCA-3)⁺ injection volume is based on lesion size:

- > 5 cm up to 4 mL
- > 2.5 cm to 5 cm up to 2 mL
- > 1.5 cm to 2.5 cm up to 1 mL
- > 0.5 cm to 1.5 cm up to 0.5 mL

When lesions are clustered together, they are injected as a single lesion according to the table for determination of CD1c (BDCA-1)⁺ myDC / CD141 (BDCA-3)⁺ myDC injection volume based on lesion size.

Intratumoral injections of CD1c (BDCA-1)⁺ myDC / CD141 (BDCA-3)⁺ myDC will be performed under sterile conditions. At the end of the procedure the injected site will be covered with an absorbent pad and dry dressing.

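### The myDC dosing rules in protocol v3.0 cannot all be followed within the expected cell yield, the two release lists differ, and the feasibility endpoint does not say what counts as a planned injection

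*Supplement*

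**What the plan says.** **Cell number.** Section 2.1.2 sets a threshold of 4 cm ("sum of longest diameters of injected lesions) will receive all isolated" myDC) and states no upper limit. The synopsis entry on the cell product expects a yield of 20 to 70 million cells. It limits the suspension to between 0.25 and 10 million cells/mL, and the injected total to between 1 million and 40 million.

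**Volume.** The synopsis and Section 8.3 limit the total to 4 mL and set volumes by lesion size. The relevant band reads "2.5 cm to 5 cm up to 2 mL".

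**Release.** The synopsis states "myDC cell products will need to meet the following release criteria: a minimal yield of" 10 million "myDC (total number of cells), >50% viability and >50% purity". Section 8.2 states that products "will need to meet the following release criteria: >50% cell viability and >50% cell purity", with no yield figure.

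**Endpoint.** Feasibility, a secondary endpoint in the synopsis and Section 5.4, is the "Percentage of study patients that can receive the planned" myDC injection. Section 14 sets a maximum of 6 patients. Section 14.1 refers to the original protocol for the analysis, and that document is not shown.

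**The concern.** A team following Section 2.1.2 and a team following the synopsis and Section 8.3 would give different cell numbers to the same patient from the same product. This would occur at yields the protocol itself expects. Section 2.1.2 sits in the rationale for the amendment, but it states the rule that will apply to cohort 2, so it is current text.

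The endpoint inherits the ambiguity because it turns on an injection being the planned one. If the plan is all isolated cells, a capped dose falls short of it; if the plan is the capped dose, it does not. A product that fails one release list and passes the other raises the same question. The case is a practical one: Section 7.2 gives AS01, ipilimumab and nivolumab on day 1, while the cells become available on day 2. A patient whose product fails has therefore already started study treatment and must be classified.

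**Working it through.** **Inputs**
- Concentration limits 0.25 and 10 million/mL; volume limit 4 mL; expected yield 20 to 70 million; release yield at least 10 million (synopsis).
- All-cells rule from a summed diameter of 4 cm (Section 2.1.2).
- Up to 2 mL for a lesion of more than 2.5 cm and up to 5 cm (synopsis, Section 8.3).
- At most 6 patients (Section 14).

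**1. The protocol's own limits reproduce.** Cells = volume × concentration.
- Minimum: 4 mL × 0.25 million/mL = 1 million.
- Maximum: 4 mL × 10 million/mL = 40 million.

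**2. All cells against the total cap.** To inject a yield Y in full, either the volume is at least Y/10 mL or the concentration in 4 mL is Y/4 million/mL.

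| Yield (million) | Volume needed at 10 million/mL | Concentration needed in 4 mL |
|---|---|---|
| 20 | 2 mL | 5 million/mL |
| 40 | 4 mL | 10 million/mL |
| 70 | 7 mL | 17.5 million/mL |

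Above 40 million, one limit must be broken or cells left over. At the top of the expected range, 70 − 40 = 30 million cells could not be given (70/40 = 1.75-fold). The conflict covers (70 − 40)/(70 − 20) = 60% of the width of the expected range. That is a 60% chance only if yields were uniform, an assumption the protocol does not make.

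**3. All cells against the lesion limit.** A single 4 cm lesion meets the 4 cm threshold but is limited to 2 mL: 2 mL × 10 million/mL = 20 million, the bottom of the expected range. A yield of 40 million would need 40/2 = 20 million/mL and one of 70 million would need 70/2 = 35 million/mL, against a maximum of 10. For this patient the rules clash at any yield above 20 million.

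**4. Release lists side by side.** A product with adequate viability and purity but fewer than 10 million cells fails the synopsis list. It meets every criterion written in Section 8.2. The lists agree at 10 million or more, hence across the whole expected range.

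**5. Effect on the endpoint.** One patient in six is 1/6 = 16.7 percentage points. Exact (Clopper-Pearson) 95% intervals:
- 6/6 = 100% (54.1 to 100)
- 5/6 = 83.3% (35.9 to 99.6)
- 4/6 = 66.7% (22.3 to 95.7)

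**The case against.** The strongest reply is that little depends on this. Feasibility is secondary and descriptive, and no sample size or decision rule in the text shown uses it. A patient given 40 of 70 million cells would ordinarily be said to have received the injection. Sections 2.1.1 and 8.2 refer to the IMPD, which may hold the release specification, and the original protocol may define the endpoint; neither is shown. Section 8.2 omits a minimum yield but does not say that there is none.

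Much of this stands. It limits the release-list point to an omission to be aligned, with consequences only below the expected yield. It does not remove the upper-end conflict, because an outside document cannot make incompatible instructions in this one compatible.

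A reader might also infer a 10-fold contradiction at the low end, since the synopsis asks for 10 million cells at release and then gives "A minimal total of" 1 million injected. The documents do not support that. The first figure is a yield and the second an injected amount, and dosing is by lesion size. A 10 million product in 4 mL is 10/4 = 2.5 million/mL; a 1 cm lesion may receive up to 0.5 mL, or 1.25 million cells, and both rules are met.

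Nor is the dose description uninterpretable: the number and volume of cells given are already a secondary endpoint (treatment disposition), and different doses for different lesion sizes are intended.

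**Conclusion.** The point holds for the upper end. The rules conflict for any yield above 40 million once the all-cells rule applies, and above 20 million for a single 4 cm lesion, against an expected yield of 20 to 70 million. For that lesion a reader might quote a 3.5-fold gap (70/20). That figure takes 70 million as deliverable, which the synopsis maximum excludes; against that maximum the gap is 40/20 = 2-fold.

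The release lists differ, with no consequence unless a yield falls below 10 million. The feasibility endpoint is under-defined in the text shown, by 16.7 points per disputed patient if all 6 are treated. How many patients would be disputed cannot be derived from the documents. It would be too strong to say that the endpoint has no meaning: a patient who receives cells under rules that agree is classified without difficulty.

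The conclusion rests on the protocol's own expected yield and on reading Section 2.1.2 as current. This should be corrected, but it does not undermine the trial's primary safety aim.

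**What to change.** Reconcile the synopsis and Sections 2.1.2, 8.2 and 8.3 into one set of release criteria and one rule for minimum and maximum cells and volume, including what happens when the yield exceeds what may be injected. The clinical and manufacturing teams choose the rule; no view is taken here on which figure is right. The volume and concentration printed beside the minimum injected total can be checked at the same time.

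Then define the planned injection in the feasibility endpoint by those rules: say whether a dose limited by the cap counts as planned, and count patients whose product fails release as not feasible. Stating the denominator from the start of leukapheresis, not replacing patients and reporting an exact interval would help the reader, but these are optional.

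The cost is protocol wording, with no added patients or procedures. The feasibility percentage may come out lower, because failed products count against it.
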